## SPECIFIC AIMS AND HYPOTHESES

**Aim 1:** To evaluate the behavioral and psychological appeal of e-cigarettes among 40 chronic smokers with smoking-related cancers.

**Hypothesis 1 (H1):** Greater than 50% of study participants will report daily e-cigarette use at each assessment during the 9 weeks that e-cigs are provided, and mean satisfaction with e- cigarettes will be >4 on a 5-point scale. In a parallel process growth model for e-cigarette and cigarette use, there will be a significant negative correlation of growth slopes.

**Aim 2:** To evaluate the effect of e-cigarettes on biological markers of combusted tobacco toxicity.

**Hypothesis 2 (H2):** After 9 weeks, mean expired breath CO2 and urine NNAL will be reduced.

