HALO manufactures its e-cigarette and the nicotine solutions in the United States. The HALO solution e-cigarettes contain 0, 12, 18, 24, or 36 mg/ml nicotine. We have been advised to begin our participants with 18mg/ml and move up or down based on patient preference. E-cigarette liquid also comes in many flavors, and we have decided to allow participants to choose from four options. Halo has agreed to provide us with the names of their 4 highest selling liquids. They have shared an ingredients list with the Drs. [name] and [name] for the purposes of adverse event monitoring and in the event that our IRB members request information about the ingredients.

Figure 6. Starter kit for the Halo Triton tank.

Coordinators will assess participants at baseline and weeks 3, 6, 9, and 12. Although most of our patients are expected to have completed their therapy, the schedule is designed to integrate with return schedules for many chemotherapeutic regimens, if possible. We have considered the concern that chemotherapy could affect cigarette consumption or excretion of nicotine metabolites. According to our clinicians, the current chemotherapy regimens for these cancers are not associated with severe symptoms, such that patients rarely decrease their smoking during treatment. Nevertheless, we will assess the severity of 6 common chemotherapy side effects at each visit so that may be entered as a covariate in our analytic models. Regarding metabolites, for nicotine, the major metabolite cotinine is formed via CYP2A6 and CYP2B6 metabolism, and the traditional cytotoxic chemotherapeutic agents used in the cancer treatment are not known to affect the activity of these CYP450 /UGT enzymes significantly. Additionally, cyclical cytotoxic chemotherapy is not given every day throughout a cycle. The most well characterized carcinogens of smoking so far are NNK (4-(methylnitrosamino)1(3-pyridyl)-1-butanone) and NNAL (4-(methylnitrosamino)1(3-pyridyl)-1-butanol). These carcinogens are also metabolized by some of the same enzymes that metabolize nicotine including CYP2A6, UGT2B10, UGT1A4 and CYP2A13, so these should not be affected by most chemotherapeutic regimens.

Coordinators will assess eligibility, collect specimens, administer CO2 measurements and administer the surveys during the baseline and follow up visits.

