### Qualitative Analysis

A follow up interview will be conducted at week 9. The interview will be transcribed and a thematic analysis will be conducted to evaluate common issues encountered by smokers with cancer patients who use e-cigarettes. Thematic analysis consists of examination of text by identifying and grouping themes, followed by coding, classifying, and developing categories. Transcripts are uploaded into a qualitative analytic software program and analyzed using Atlas.ti, a qualitative coding program. Co-investigator [name] has experience using similar qualitative methods to interview health professionals. She will supervise the coders, staff at the Centers for Health and Aging at Dartmouth who have been trained to perform similar analyses in other studies.

*Substitution assessment:* The proportion of participants who report use of e-cigarettes during each follow-up visit during treatment will also be computed (along with a 95% confidence interval). This proportion is expected to be at least 0.5. With 40 participants, width of a 95% confidence interval around this proportion will be at most 0.32. The satisfaction with e- cigarettes (averaged across 3 treatment assessments) will be summarized among participants using descriptive statistics and the amount of e-cigarette product returned at each follow-up period will be summarized across the treatment period.

To explicitly test the substitution/replacement mechanism of e-cigarettes, we will perform an exploratory parallel process growth model fit within a structural equation modeling framework. In this model the trajectory over time of both frequency/quantity of cigarette use and frequency/quantity of e-cigarette use will be modeled assuming individual-level latent intercept and slope (i.e., latent growth curve model). A significant negative association between the latent slope of e-cigarettes and the latent slope of combustible cigarettes would be consistent with the replacement/substitution hypothesis. The model provides an explicit statistical test of the hypothesis that, as e-cigarette usage increases, combustible cigarette usage decreases. Power for this analysis is computed as that for an individual-level correlation coefficient assuming 40 participants. There will be at least 80% power to detect a correlation that is at least -0.4 between these two individual-level slopes. Figure 7 shows a diagram of the parallel process growth model.

n

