**Toxicity Assessment:** Our measures of toxicity, urine NNAL, 1-HOP and CO2 will be compared between the baseline and 9-week assessments via paired t-test. For NNAL, assuming a standard deviation of change in this measure of 3.8 pmol/mg creatinine (as was seen in Joseph et al. 2008), with 40 participants, this test will have 80% power at the two-sided 0.05 significance level to detect a change from baseline of 1.7 pmol/mg creatinine. There is not enough information available on 1-HOP to perform a test of power, so analysis of this metabolite is considered exploratory. For expired CO, assuming a standard deviation of change in this measure of 17.0 ppm, with 40 participants, a paired t-test comparing baseline to 9-week will have 80% power at the two-sided 0.05 significance level to detect a change from baseline that is 7.7 ppm. Additionally, since CO2 will be measured several times throughout the treatment period, the trajectory of change over time in this measure will be modeled via linear mixed effects models including random intercept and slope terms to account for repeated observations within individual. With repeated measurements of CO, the power for the mixed model will be greater than that of the paired t-test of change from baseline to detect this change over time.

We will also evaluate toxicity by analyzing cotinine level to assure that the adverse effect of increased cotinine (resultant from increased e-cigarette usage without similar decrease in combustible cigarettes). To do this, we will compute the number of participants with an increase in cotinine over the course of the study and consider this an adverse event. With 40 participants, confidence intervals around this adverse event percentage will be at most 0.32 percentage points. The table below gives the probability of observing at least 1 participant with an increase in cotinine given different true percentage of participants with this adverse event. For example, if the population-wide true percentage of participants with cotinine increase is 0.5%, then the probability of observing at least 1 of the 40 study participants with an increase is 0.18.

True percentage of participants with increase cotinine	Probability of observing at least 1 adverse event (increase in cotinine)
0.5%	0.18
1%	0.33
2%	0.55
5%	0.87
10%	0.99

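### The 80% power for a slope correlation of -0.4 ignores error in the latent slopes and states no alpha or sidedness; error-free power is about 82% one-sided but only 73% two-sided

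*Combined protocol and SAP*

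**What the plan says.** In Statistical Analysis and Power Considerations, the Substitution assessment paragraph introduces the model: "we will perform an exploratory parallel process growth model fit within a structural equation modeling framework". Each participant has a latent intercept and a latent slope for cigarette use and for e-cigarette use, and the test concerns the association between the two slopes. The power basis is "Power for this analysis is computed as that for an individual-level correlation coefficient assuming 40 participants". The result is "There will be at least 80% power to detect a correlation that is at least -0.4 between these two individual-level slopes". The paragraph gives no slope variance, residual variance, slope reliability, alpha, sidedness or allowance for dropout.

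Three other places bear on this:

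- Specific Aims and Hypotheses makes the correlation part of Hypothesis 1: "there will be a significant negative correlation of growth slopes". The Primary outcomes list also includes the correlation between the two changes in use.
- Study Design fixes the data behind each slope: "Coordinators will assess participants at baseline and weeks 3, 6, 9, and 12". Product is supplied for nine weeks, so four of the five visits fall within the supply period.
- The Toxicity Assessment paragraph states a significance level, but for the paired t-tests: "this test will have 80% power at the two-sided 0.05 significance level".

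**The concern.** A power formula for a plain correlation needs one exactly known pair of values per person. Here each value is a slope fitted to a few visits of mainly self-reported use, so part of the spread between fitted slopes is noise. A latent growth model removes the bias that this noise puts into the estimated correlation. It does not restore the lost information, so the standard error grows and power falls.

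The missing alpha is a separate gap. At n = 40 and a correlation of -0.4, the choice of one or two sides decides whether the figure passes 80% even before slope error is considered.

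What is at stake is how well the study can address one of its listed primary outcomes. A pilot that informs a larger trial should not carry a power figure that its own model can reach only under near-perfect measurement.

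**Working it through.** **Inputs from the plan.** n = 40; correlation -0.4; claimed power at least 80%; visits at weeks 0, 3, 6, 9 and 12.

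**Assumptions.** Alpha 0.05, shown one-sided and two-sided. Slope reliability is the same for both processes, and the visit errors of the two processes are independent. The documents give no value for reliability.

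**1. Reproducing the plan's figure (error-free slopes).** Fisher z: power = Φ(atanh(|r|)·√(n−3) − z).

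atanh(0.4) = 0.4236 and √37 = 6.083, so the product is 2.577.

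- One-sided (z = 1.645): Φ(0.932) = 82.4%.
- Two-sided (z = 1.960): Φ(0.617) = 73.1%.

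Simulating the ordinary t-test for a correlation gave 83.4% and 74.2%. A fixed-x noncentral t calculation gave 76.7% two-sided, still short of 80%. The plan's figure therefore reproduces only one-sided.

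The smallest |r| with 80% power is tanh((z + 0.842)/6.083):

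- One-sided: tanh(0.4088) = 0.387.
- Two-sided: tanh(0.4606) = 0.431.

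For r = 0.4, 80% power needs 38 participants one-sided or 47 two-sided.

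**2. Adding slope error.** The correlation between fitted slopes is r × √(rel₁·rel₂), which is 0.4 × rel when the two reliabilities are equal. The same formula then gives:

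| Assumed reliability | Attenuated r | Two-sided | One-sided |
|---|---|---|---|
| 1.0 | 0.40 | 73% | 82% |
| 0.9 | 0.36 | 63% | 74% |
| 0.8 | 0.32 | 52% | 65% |
| 0.7 | 0.28 | 42% | 54% |
| 0.6 | 0.24 | 32% | 44% |
| 0.5 | 0.20 | 23% | 34% |

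Example at 0.8: atanh(0.32) × 6.083 = 0.3316 × 6.083 = 2.017. Then Φ(2.017 − 1.960) = 52% and Φ(2.017 − 1.645) = 65%.

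**3. Does the latent model recover the loss?** A bivariate growth model was simulated with 4 visits, n = 40, true correlation -0.4 and 250 trials per setting. The test was a two-sided 0.05 likelihood-ratio test of the slope covariance. Power was 71%, 56%, 36% and 15% at reliability 0.95, 0.8, 0.6 and 0.4, with a Monte Carlo standard error of about 2 to 3 points. The formula gives 68%, 52%, 32% and 16% at the same values. The growth model does about as well as correlating the fitted slopes, and no better in any way that matters.

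**4. When does the stated 80% hold?**

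- One-sided: 0.4 × rel ≥ 0.387, so rel ≥ 0.97.
- Two-sided: 0.4 × rel ≥ 0.431 would need rel above 1, so never.

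**5. Latent correlation needed for 80% power** (smallest |r| divided by reliability):

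- Two-sided: 0.431/0.8 = 0.54; 0.431/0.5 = 0.86.
- One-sided: 0.387/0.8 = 0.48; 0.387/0.5 = 0.77.

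**The case against.** The plan labels this model exploratory, the study is a feasibility pilot, and nothing in the documents derives the sample size of 40 from this correlation. The hypothesis is directional, so a one-sided test is a fair reading, and on that reading the calculation reproduces at 82%. The Timeline Follow-Back questionnaire and the check of reported use against returned product could make the use data fairly reliable.

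Much of this stands, and it limits the point in three ways.

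- **The size of the loss.** A reader might infer that the true power is some 25% to 55%. That follows only from an assumed reliability of about 0.5 to 0.8 and a two-sided test. The documents fix neither. At reliability 0.9 power is 63% two-sided or 74% one-sided.
- **The cause.** A reader might blame the whole shortfall on slope error. On a two-sided basis about 7 points (80% to 73%) come from sidedness alone, before any slope error. Nor does the claim depend on perfect reliability: one-sided it holds down to about 0.97, and two-sided it fails even at 1.
- **The consequence.** A reader might infer that the plan would treat a null result as evidence against substitution. No section says so. The plan says only that a significant negative association would be consistent with substitution.

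The exploratory label does not remove the point. The same correlation sits in Hypothesis 1 and among the primary outcomes, and the plan attaches a definite power figure to it.

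**Conclusion.** The power statement is wrong as written, in a limited sense. It uses a formula for observed pairs on a model with latent slopes, and it omits the alpha and sidedness on which the 80% depends. Without any assumption about reliability, the claim fails at two-sided 0.05 (about 73%) and passes at one-sided 0.05 (about 82%) only if the slopes are almost free of error. Slope error lowers power in either case, so the direction is certain. The amount is conditional: 63%, 52% and 23% two-sided, or 74%, 65% and 34% one-sided, at assumed reliability 0.9, 0.8 and 0.5, taken as equal for both processes. All these figures use the full 40 participants, and any dropout would lower them further.

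**What to change.** Replace the 80% sentence with text that does four things:

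1. States alpha and sidedness for this test.
2. Gives the error-free power for a correlation of -0.4 as an upper bound: about 73% if two-sided 0.05, or about 82% if one-sided 0.05.
3. Gives power at slope reliability 0.5 to 0.9, labelled as an assumption: about 23% to 63% two-sided, or 34% to 74% one-sided. Adds the latent correlation needed for 80% power: about -0.54 at reliability 0.8 and -0.86 at 0.5 two-sided, or about -0.48 and -0.77 one-sided.
4. Says that a non-significant result in this exploratory model is not evidence of no substitution.

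The cost is a less favourable stated figure. Data collection and sample size do not change.

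### Power for a slope correlation of -0.4 with 40 participants is about 73-74% at two-sided 0.05, not 80% or more

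*Combined protocol and SAP*

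**What the plan says.** The substitution assessment, under Statistical Analysis and Power Considerations, plans a parallel process growth model for cigarette and e-cigarette use. The quantity tested is the association between the two latent slopes. The power basis is given in one sentence: "Power for this analysis is computed as that for an individual-level correlation coefficient assuming 40 participants". The result follows: "There will be at least 80% power to detect a correlation that is at least -0.4 between these two individual-level slopes". Neither a significance level nor a sidedness is given for this test. I read the wording as a correlation of magnitude 0.4 or more in the negative direction.

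The toxicity assessment that follows does state its level, twice. For NNAL, "this test will have 80% power at the two-sided 0.05 significance level to detect a change from baseline of 1.7 pmol/mg creatinine", and for expired CO the paired t-test "will have 80% power at the two-sided 0.05 significance level to detect a change from baseline that is 7.7 ppm".

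On status, the plan says "we will perform an exploratory parallel process growth model fit within a structural equation modeling framework". Hypothesis 1 nevertheless includes the prediction that "there will be a significant negative correlation of growth slopes", and the primary outcomes list the correlation between change in e-cigarette use and change in cigarette use.

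**The concern.** A simple correlation of 0.4 tested at two-sided 0.05 needs more than 40 subjects for 80% power, so the stated figure looked too high for the method the plan names.

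If it is too high, a true correlation of -0.4 would be missed about 26-27% of the time, where the text promises no more than 20%. The growth model is presented as the direct test of whether e-cigarettes replace cigarettes, and the study is a pilot for a larger randomized trial. A reader who trusts the stated power would take a null result as stronger evidence against substitution than it is.

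**Working it through.** **Inputs.** From the substitution assessment: n = 40, correlation of magnitude 0.4, power as for a simple correlation coefficient. From the toxicity assessment: two-sided 0.05, with SD of change 3.8 pmol/mg creatinine (NNAL) and 17.0 ppm (CO).

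**Step 1. Which convention do the plan's other power figures follow?** For a paired t-test with n = 40 and 80% power, the detectable standardized change is 0.4543 at two-sided 0.05 and 0.4002 at one-sided 0.05.

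| Measure | Plan | Two-sided 0.05 | One-sided 0.05 |
|---|---|---|---|
| NNAL (pmol/mg creatinine) | 1.7 | 0.4543 × 3.8 = 1.73 | 0.4002 × 3.8 = 1.52 |
| CO (ppm) | 7.7 | 0.4543 × 17.0 = 7.72 | 0.4002 × 17.0 = 6.80 |

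The plan's figures reproduce at the two-sided level they declare. The hypothesis behind them is directional ("urine NNAL will be reduced"), so a directional hypothesis did not lead to one-sided testing there.

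**Step 2. Power for the correlation.** With Fisher's z, power = Φ(atanh(|r|) × √(n − 3) − z_crit).

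- atanh(0.4) = 0.4236 and √37 = 6.083, so the product is 2.577.
- Two-sided 0.05: Φ(2.577 − 1.960) = Φ(0.617) = **73.1%**.
- One-sided 0.05: Φ(2.577 − 1.645) = Φ(0.932) = **82.4%**.

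Other methods at two-sided 0.05:

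| Method | Power |
|---|---|
| Fisher z | 73.1% |
| Fisher z, t-based critical r (0.312) | 74.0% |
| Fisher z, bias-corrected | 74.2% |
| Exact distribution of r, bivariate normal | 74.2% |
| Simulated t-test of r, 400,000 data sets | 74.3% |
| Noncentral t treating one variable as fixed | 76.7% |

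The last row does not suit two random slopes and is shown only as the most generous variant. It is still below 80%. At one-sided 0.05 the exact figure is 83.4%.

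**Step 3. What would give 80% at two-sided 0.05?**

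- Detectable correlation at n = 40: tanh((1.960 + 0.842)/6.083) = tanh(0.461) = 0.431 by Fisher z; 0.426 by the exact method.
- Sample size at |r| = 0.4: ((1.960 + 0.842)/0.4236)² + 3 = 46.7, so 47 by Fisher z. The exact method gives 46 (80.2%; 45 gives 79.3%).

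**Step 4. Fewer contributing participants.** The documents give no dropout figure, so these numbers are assumed for illustration. At two-sided 0.05, 36 contributing gives 68% (Fisher z) to 69% (simulation), and 32 gives 63% to 64%.

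**The case against.** The strongest counter-argument is that the plan never states a level for this test. Hypothesis 1 is directional, and at one-sided 0.05 the sentence is correct: power is 82.4-83.4%, and 80% is reached at a correlation of about 0.39 (Fisher z: tanh((1.645 + 0.842)/6.083) = 0.387). On that view the fault is an undeclared assumption, not wrong arithmetic. Reproducing 1.7 and 7.7 shows only that the toxicity paragraph used the level it declares; it does not prove what was used one paragraph earlier. This stands to the extent that two-sided 0.05 is an inference for the correlation test. It is a strong inference, because no other level appears in the plan and the plan's other directional hypothesis is tested two-sided. The one-sided reading also needs an edit, since the test would have to be declared.

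A second argument is rounding: 0.43 to one decimal is 0.4, in the same style as 1.73 to 1.7. That may explain how the figure arose, but it does not make a promise of 80% or more true at 0.4. The rounded NNAL and CO changes still carry 78.8% and 79.8% power by the t-test, losses of 1.2 and 0.2 points against 6 to 7 here.

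A third is importance. The model is exploratory, no passage derives the sample size of 40 from this calculation, and no decision rule depends on it. The documents also do not say how the slope result would be used in planning the larger trial. All of this limits the consequence. It does not remove the need for an accurate power statement on a component of Hypothesis 1 and the primary outcomes.

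**Conclusion.** The concern holds. By the plan's named method and at the only test level it states, power for a correlation of -0.4 with 40 participants is 73-74%, which is 6 to 7 points below the claim. The claim is met only by a one-sided 0.05 test that the plan does not declare.

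The conclusion rests on carrying two-sided 0.05 over from the toxicity assessment. The 73-74% also assumes that all 40 participants contribute and that each person's two slopes are known without error. Fewer contributing participants would lower the power. The figure corrects the plan's stated calculation and is not an estimate of the growth model's actual power.

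This is a misstatement to correct in an exploratory analysis that feeds a primary hypothesis. It does not call the design or the sample size into question.

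**What to change.** Replace the power sentence in the substitution assessment with wording such as:

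> With 40 participants there is about 73-74% power at the two-sided 0.05 level to detect a correlation of -0.40 between the two slopes, and 80% power for a correlation of about -0.43. This assumes that all 40 participants contribute and makes no allowance for error in estimating the slopes.

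If a one-sided 0.05 test was intended, declare it there and say why it differs from the two-sided tests in the toxicity assessment. The power claim may then stay, with the same two assumptions stated.

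The cost is one sentence and, under the two-sided reading, a less favourable stated power. No extra participants, data or model changes are needed.

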### ONLY A SMALL PROPORTION OF CANCER PATIENTS SUCCEEDED AT QUITTING SMOKING

The information from the Roswell Park study would suggest that approximately 30-40% of smokers attempt to quit at or around the time of their cancer diagnosis. A recent publication from a large, well-funded cessation service at Sloan-Kettering offering intensive cessation support, found that of over 4500 tobacco user referrals, 3430 (75%) were unreachable or refused cessation assistance. Of the over 1000 enrolled in the service, about 25% did not complete the protocol, 25% either died or were lost to follow-

up, and 43% reported no tobacco use at 6 months. In summary, the data from a large cessation service at a major cancer center suggest that these state-of-the art programs benefit only about 10% of smokers with cancer. This is, again, consistent with the findings above that suggest these individuals are heavily addicted and relatively refractory to cessation treatment, leaving about 90 percent who continue to expose themselves to smoke-derived carcinogens during the course of their therapy.

[figure not shown]
The Sloan-Kettering program assessed e-cigarette use among patients trying to quit smoking and found that as many as half of these patients were experimenting with e-cigarettes during 2013, but that e-cigarette use did not affect successful quit rates. This is becoming a common finding in population studies of e-cigarettes, in part because people receive mixed messages from the public health community regarding whether these products represent an appropriate substitute for smoking. In the present study, we will test the appeal and toxicity of e-cigarettes in smokers with cancer.

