## **TRIAL PROTOCOL**

### **STUDY DESIGN**

We will enroll 40 chronic smokers from the Norris Cotton Cancer Center and the White River Junction VAMC, approximately 15 of which will be accrued from the White River Junction VAMC. Participants will be given access to e-cigarettes for a 9-week period. Consecutive patients with stage I-IV aerodigestive tract cancers or bladder cancer who are current daily smokers will be identified two ways:

- 1) Clinic Recruitment - Potential participants will be identified by the treating physician during routine clinic visits. Patients will be advised to quit smoking as per the standard of care. Any patient wishing to quit smoking will be referred for smoking cessation counselling through the DHMC program, the White River Junction VAMC program, or their state help-line. Once eligibility is confirmed and informed consent is obtained and signed, patients will be enrolled in the study.
- 2) EMR Recruitment: In a recruitment strategy that parallels clinic recruitment, we will use the EMR to identify all potentially eligible smokers (with the diagnosis of aerodigestive tract cancers or bladder cancer) that have been seen in the NCCC in the past 3 years. EMR records will be searched by the D-HRDS Analytics Institute who will then forward a list of potential subjects to the project coordinator with their diagnoses and contact information, consistent with our partial HIPAA waiver. The project coordinator will then send this list of potential subjects to their providers to be approved to be contacted about the study. Approved potential subjects will then be contacted by mail through a letter from their NCCC oncology group. The subjects will have an opportunity to opt out of receiving a phone call through a prepaid return mailer or by calling a telephone number. If we do not hear from them in 2 weeks, we will then attempt to call them. We will attempt to call one time a week for 3 weeks. If there is no answer we will leave a brief, generic message. The call will assess their smoking status, and their willingness to quit. Nonsmokers are not eligible. If they smoke and are interested in quitting, they will be referred to their state quit line. If they are not interested in quitting at this time, they will be

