## STUDY TIMELINE AND FOLLOW-UP

The trial is designed to allow for patient visits every 3 weeks for 12 weeks. The coordinators will work with the participant and the participants' medical care teams to schedule and conduct the visits. We will contact enrolled subjects for follow-up at 6 and 12 months after enrollment. Each time, we will attempt to contact the subjects 3 times by phone over a period of 3 weeks. During the call the subject will be asked if they are still using an e-cigarette, what brand they are using, what concentration of nicotine they use, how many times a day they use it, and how often they currently smoking any combustible tobacco products.

Participants will receive free e-cigarette products for the first 9 weeks of the trial and \$20 for each visit (\$100 total). Participants that travel more than 20 miles one-way for a study-only visit (no other appointments scheduled on the day of their study visit) will be given a \$10 gas card.

Time	Baseline	3 weeks	6 weeks	9 weeks	12 weeks
Activity	Consent; survey; ecig instruction; urine; CO	Survey; ecig refill; urine; CO	Survey; ecig refill; CO	Survey; qualitative interview; urine; CO	Survey; CO
Compensation	\$20	\$20	\$20	\$20	\$20

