The NCCC Clinical Pharmacology Shared Resource (CPSR) will conduct assays of urine for smoke-related carcinogens. Urine samples (at least 20 mL) will be collected at the study defined time points from study participants in standard urine containers. These will be delivered to the NCCC CPSR, divided into 5 mL aliquots and stored at -20°C or below until analysis. Urine aliquots will be assayed in batches based on the published assays for urine nicotine, cotinine, 4- (methylnitrosamino)-1-(-3pyridyl)-1butanol (NNAL) and 1-hydroxy naphthalene (1-HOP) concentrations. These assays can and will be established and validated in the NCCC CPSR using the LC-MS/MS and HPLC-Fluorescence services available in the CPSR.

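### The week-9 NNAL and CO power figures assume no loss among the 40 enrolled, and the only stated NNAL analysis leaves out week-3 urine and anyone without a week-9 sample

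*Combined protocol and SAP*

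**What the plan says.** All references are to the combined protocol and SAP.

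- **Enrolment.** Study Design: "We will enroll 40 chronic smokers from the Norris Cotton Cancer Center" and a second site, 40 in total.
- **Test.** In the Toxicity Assessment paragraph of the statistical section, NNAL, 1-HOP and CO (printed in places as CO2) "will be compared between the baseline and 9-week assessments via paired t-test".
- **Power, NNAL.** SD of change 3.8 pmol/mg creatinine, change to detect 1.7: "with 40 participants, this test will have 80% power at the two-sided 0.05 significance level".
- **Power, CO.** SD of change 17.0 ppm, change to detect 7.7 ppm: "with 40 participants, a paired t-test comparing baseline to 9-week will have 80% power".
- **1-HOP.** No power calculation; labelled exploratory.
- **Mixed model.** Random intercept and slope, for CO only, with the remark that "the power for the mixed model will be greater than that of the paired t-test".
- **Urine.** The visit table in Study Timeline and Follow-up schedules it at baseline, week 3 and week 9; the week-3 entry reads "Survey; ecig refill; urine; CO". Outcomes Assessment says "Urine aliquots will be assayed in batches based on the published assays for urine nicotine, cotinine", and the sentence goes on to NNAL and 1-HOP.
- **Retention.** No expected loss, replacement rule or missing-data method is given. The only retention figure, in the background, is from a cessation service for smokers with cancer: "about 25% did not complete the protocol, 25% either died or were lost" to follow-up, with outcome at 6 months.

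**The concern.** The number enrolled and the number of analysed pairs are both 40, so the stated power leaves no room for a single missing week-9 value. Participants may have stage IV disease and may be on anti-cancer agents, so some loss is a reasonable thing to plan for.

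The analysis matters at least as much as the power. Lower NNAL after 9 weeks is half of Hypothesis 2, and NNAL is listed among the primary outcomes. A paired t-test uses only people with both values. In a single-arm study no control group offsets a shift in who remains: if people with a smaller early fall leave more often, the estimated fall is too large; if people with a larger fall leave, it is too small. The week-3 urine could correct part of this, but no analysis of week-3 NNAL is stated. The pilot is meant to inform a larger trial, so a shifted estimate could carry into its planning.

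**Working it through.** **1. Reproduce the plan's figures.** For n pairs, change d and SD of change s, power is the probability that a noncentral t variable with n − 1 degrees of freedom and noncentrality d√n/s falls beyond the two-sided 0.05 limits. With n = 40:

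- NNAL: 1.7 × √40 / 3.8 = 2.83; power 78.8%; change detectable with 80% power 1.726.
- CO: 7.7 × √40 / 17.0 = 2.86; power 79.8%; change detectable with 80% power 7.722.

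These round to the stated 1.7 and 7.7. The normal approximation n = (s(1.960 + 0.842)/d)² gives 39.2 and 38.3. The arithmetic is sound for 40 complete pairs.

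**2. Allow for loss.** The loss rates are assumptions. The SDs and changes are the plan's.

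| Loss | Pairs | Power at 1.7 (NNAL) | Power at 7.7 (CO) | 80% detectable, NNAL | 80% detectable, CO |
|---|---|---|---|---|---|
| 0% | 40 | 79% | 80% | 1.7 | 7.7 |
| 10% | 36 | 74% | 75% | 1.8 | 8.2 |
| 15% | 34 | 72% | 73% | 1.9 | 8.4 |
| 20% | 32 | 69% | 70% | 1.9 | 8.7 |
| 25% | 30 | 66% | 67% | 2.0 | 9.0 |

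**3. Bias if loss follows early response.** This was simulated with 40 enrolled, 15% loss, and odds of leaving 1.5 to 2 times higher per SD smaller week-3 fall. Results are averaged over nine settings (three variance splits by three shapes of fall). The true NNAL fall is 1.7.

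- Everyone leaves after week 3: the paired estimate averages 1.85 to 1.95. At odds ratio 2 the false-positive rate for NNAL averages 6.7%.
- Half leave before week 3 for unrelated reasons: 1.78 to 1.84, with false positives of 5.1% to 5.5%.
- Overstatement: from 1.78/1.7 (5%) to 1.95/1.7 (15%).
- Scale: the standard error with 34 pairs is 3.8/√34 = 0.65, so a bias of 0.08 to 0.25 is about 0.1 to 0.4 standard errors.
- A repeated-measures model on weeks 0, 3 and 9 with estimated unstructured covariance averages 1.70 to 1.71, with 4.2% to 4.6% false positives.

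**4. Power gained by that model.** At 15% random loss, simulated power is 73.5% if everyone leaves after week 3, or 71.7% if half leave before, against 71.4% for the paired test. With complete data there is no gain.

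**5. The CO power sentence.** Suppose all of the fall occurs by week 3. With complete data, a straight line over weeks 0, 3, 6 and 9 has slope (−1.5 + 1.5 + 4.5)/45 = 0.1 of the fall per week, so it fits 9 × 0.1 = 90% of the fall. The linear model's power is then 72% to 74% against 80% for the t-test. If the fall is linear it is 81% to 83%. At 15% random loss with all of the fall by week 3 it is 74% to 77% (71% to 72% if half leave before week 3) against 73%. So the sentence depends on the shape of the fall.

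**The case against.** Much of the case on the other side stands.

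- **Retention may be good.** The endpoint is at 9 weeks. Visits are paid and arranged with care teams, and entry requires ability to attend. Surgery or radiation planned within 9 weeks excludes, and most patients are expected to have finished therapy. None of this shows zero loss, but the 15% used here has no support in the documents. A reader might take the cessation service's two 25% figures as a forecast. They are not: that setting is different and its follow-up longer.
- **The week-3 NNAL assay is inferred.** The assay text names no visit, and week-3 urine could also serve propylene glycol or cotinine. Assay for NNAL is the natural reading, not a written commitment. Likewise, exclusion of people without week-9 urine follows from the paired test and is not spelled out.
- **The bias scenario is assumed.** Loss rate, odds ratios and timing are chosen inputs, and loss driven by an observed week-3 value is the case a repeated-measures model handles best.
- **The effect is modest.** At 15% loss the detectable changes move from 1.7 to 1.9 and from 7.7 to 8.4.
- **CO is largely covered.** The paired CO estimate is open to the same kind of shift, but the planned mixed model keeps people with partial data. The power sentence fails mainly when data are complete, so it is a minor matter.

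What these points do not answer is that a primary outcome has no missing-data rule, and that its only stated test passes over a scheduled sample.

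**Conclusion.** The point holds in a limited form. The stated 80% requires a week-9 value from everyone enrolled; at an assumed loss of 10% to 25%, power falls to 74%–66% for NNAL and 75%–67% for CO. For NNAL, and for 1-HOP as an exploratory marker, the only stated analysis uses completers and omits week 3. If loss depends on early response, the paired NNAL estimate is off by about 5% to 15% under the assumptions tried, and by less when many leave before week 3.

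Two stronger readings are not supported. One is that the power calculation is wrong or the study too small: the figures are correct for 40 pairs, and a single-arm pilot needs a stated loss assumption rather than more participants. The other is that the CO result is compromised: CO already has a model that uses partial data. This is a worthwhile, inexpensive improvement, not a defect that undermines the study.

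**What to change.** 1. **NNAL analysis.** Analyse NNAL (and 1-HOP, exploratory) at weeks 0, 3 and 9 with a mixed model for repeated measures: visit as a categorical factor, unstructured covariance, small-sample degrees of freedom (for example Kenward-Roger), and week 9 minus baseline as the contrast. Keep the paired t-test as a check. Report the number, timing and reasons for missing week-9 values. Confirm in the assay section that week-3 urine is assayed for NNAL.
2. **Power statement.** Without enrolling more, write for example: *Of 40 enrolled, assuming 15% (illustrative; range 10%–25%) lack a week-9 value, 34 pairs give 80% power to detect changes of 1.9 pmol/mg creatinine and 8.4 ppm.*
3. **Optional.** Make the CO mixed-model power sentence conditional on an approximately linear fall. Keep the planned CO analyses; no second CO model is needed.

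**Cost.** Only wording changes, with visits and samples already scheduled, provided the week-3 NNAL assay is confirmed. The power figures look slightly less favourable, a covariance structure must be specified, and the model assumes data are missing at random. It brings little or no gain in power. It does not correct for loss before week 3 or for loss driven by unobserved values.
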